## VI. BIOSTATISTICAL ANALYSIS

### A. Specific data variables

The specific data elements collected at each visit are as follows:

**1) Screening visit data elements:** This visit will focus on assessing variables related to the inclusion and exclusion criteria. Variables collected during this visit will include:

- First and last name
- Date of birth
- Native language and self-reported comfort communicating in English among non-native speakers
- Ever smoked  $\geq 100$  cigarettes
- Current cigarettes per day
- Saliva cotinine level  $\geq 30$  ng/mL, based on point-of-care testing
- Prior serious allergic reactions to varenicline

- Currently pregnant, planning to become pregnant, or breastfeeding
- Readiness to try quitting smoking within the next 3 months
- Prior experience with homelessness
- Presence of BHCHP electronic health record
- Name of BHCHP PCP (and if PCP has been seen within the past year)
- History of psychiatric hospitalization within the past 3 months
- Suicidal ideation and behavior, based on the C-SSRS
- Among individuals who are eligible and wish to schedule an enrollment visit or who are ineligible but would be interested in attempting screening again in the future, we will collect their current phone number (if any) to facilitate communication about the enrollment visit

**2) Enrollment visit data elements:** When individuals present for enrollment, we will confirm that they have previously screened eligible for the study. For those who wish to enroll in the study, we will collect additional demographic and contact information:

- Gender
- Pronouns
- Social security number
- Current residence or place where sleeping at night
- Current phone number (if any); confirm/update number if previously collected at screening visit
- Emergency contact information
- BHCHP medical record number
- Insurance coverage listed within BHCHP electronic health record

We will also conduct a baseline survey assessing the following variables at the time of enrollment: *Italicized* measures will be collected during follow-up surveys at weeks 12 and 24:

Domains	Measures
Sociodemographic	Race/ethnicity; education; health insurance (all based on items from the 2003 HCH User Survey  and our prior survey work  )
Homelessness	Homelessness episodes and duration; living situation; past-month subsistence difficulties
Mental/physical health	General health status (SF-1); single item measurement of cigarette craving; chronic medical conditions; Domains related to COVID-19, including diagnosis and symptom history, change in quitting motivation, and receipt of the COVID-19 vaccine; AUDIT, DAST-10; past 3-month drug use inventory; PHQ-9; GAD-7; MDQ; PSQ
Tobacco use	Age of initiation; past quit attempts (<math>\geq 24</math> hours) ; use of cessation aids; use of e-cigarettes or vape products; cigarettes/day ; Fagerstrom Test for Nicotine Dependence  ; 10-point importance and confidence scales ; stage of change ; Contemplation Ladder ; social support for quitting  ; past month use of alternative tobacco products 

**3) On-treatment monitoring visit data elements:** The following variables will be collected at the timepoints specified in parentheses. If participants miss their week 12 monitoring visit, the underlined elements will be asked during the follow-up survey visit up to 2 weeks later.

- Point-of-care saliva cotinine level (every monitoring visit, per Figure 3)
- Date and time last smoked all or most of a cigarette (every monitoring visit)
- Date and time of last puff of cigarette (every monitoring visit)
- Number of smoking days in the past 7 days (every monitoring visit)
- Average number of cigarettes per day (every monitoring visit)
- Use of vape or e-cigarette in past 7 days (every monitoring visit)
- Use of other tobacco products in past 7 days (every monitoring visit)
- Single item measurement on cigarette craving (every monitoring visit)
- Past week use of varenicline prescribed by study clinician (every monitoring visit)
- Average number of varenicline pills taken per day (if applicable, based on whether the participant is prescribed varenicline by the study clinician; every monitoring visit)
- Use of other quit smoking aids (every monitoring visit)
- Side effects to varenicline, including abnormal dreams, aggressive/erratic behavior, headaches, nausea, sleep disturbance/insomnia, vomiting, and other (if applicable; every monitoring visit)
- Suicidal thoughts, intention, and behaviors since last study visit, as measured by a modified version of the C-SSRS (if applicable; every monitoring visit).
- Other adverse events not related to varenicline if reported by participant (every monitoring visit)
- All items italicized in the baseline survey table above at 12 weeks, or within 2 weeks post
- Saliva cotinine level from results of laboratory cotinine testing at 12 weeks, or within 2 weeks post

**4) Post-treatment outcome assessment visit data elements:** The following variables will be collected at 24 weeks, or within 2 weeks post, unless otherwise specified in parenthesis.

- Point-of-care saliva cotinine level (incentive participants only)
- Date and time last smoked all or most of a cigarette
- Date and time of last puff of a cigarette
- Number of smoking days in the past 7 days
- Number of quit attempts in the past 3 months
- Use of cessation aids
- Use of vape or e-cigarette in the past 7 days
- Use of other tobacco products in the past 7 days
- All items italicized in the baseline survey table above
- Laboratory saliva cotinine level

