**5) Coaching session data elements: Baseline, 2, 4, 8, and 12 weeks (or within 1 week)**

- Confidence to quit smoking (or to stay quit)
- Importance of quitting smoking (or staying quit)
- Past-month quit attempts
- Summary of coaching session, including experiences delivering the intervention including the ease of delivery (including the length, scheduled time); the apparent acceptability and relevance; comprehension of the material by the participants; and factors that impeded or assisted in the delivery, and any issues related to safety or potential harms that emerge.

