#### B. Drug side effects and toxicities

Participants will be offered a prescription for varenicline. Common side effects of varenicline are nausea, sleep problems, constipation, gas, and vomiting. Other possible, but less common, side effects include cardiovascular (chest pain, hypertension, tachycardia), sleep walking, allergic reactions, or serious skin reactions. Participants who are taking varenicline prescribed by the study clinician will be assessed for varenicline side effects and suicidality at each on-treatment monitoring visit. Procedures for addressing participants with significant side effects and suicidality are described below (section IX. D.).

In June 2021, Pfizer announced a halt in global distribution of varenicline (brand name: Chantix) and a voluntary recall of selected lots after finding heightened levels of N-nitroso-varenicline (a nitrosamine compound) in some pills. Although the risk posed by N-nitroso-varenicline is uncertain, nitrosamine compounds in general are considered carcinogenic when exposure occurs in sufficient doses over prolonged periods of time. The nitrosamine levels found in Pfizer's varenicline product exceeded the FDA's acceptable intake limit of 37 ng per day. In September 2021, Pfizer extended its recall to all lots of varenicline.

The FDA has since approved two generic versions of varenicline: one manufactured by Apotex and one manufactured by Par Pharmaceuticals. The FDA also announced that they would not object to manufacturers distributing varenicline tablets above the FDA's original acceptable intake limit of 37 ng per day but below an interim acceptable intake limit of 185 ng per day. Both of the above generic versions of varenicline distributed by Apotex and Par have levels of N-nitroso-varenicline that are within the FDA's interim acceptable intake limit.

Study staff are working closely with the BHCHP pharmacy to ensure participants receive a varenicline product that falls within these interim safe limits. During informed consent, staff will inform participants of the risk of contamination of varenicline products while also clarifying that the versions they will receive have been deemed safe by the FDA.

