During the trial, participants will be asked proactively about side effects at regular intervals during monitoring visits and encouraged to report side effects to varenicline at any time. Adverse reactions will be tracked and addressed according to the adverse event procedures outlined below. Participants will be asked to rate the severity of their side effects as none, mild, moderate, or severe. Mild reactions will be recorded and monitored, and participants will be encouraged to let study staff know if they worsen or persist. If a participant rates a side effect as moderate, study staff will ask if the participant wants to speak with a clinician. If so, the clinician will phone participants within 48 hours to assess their symptom(s) and formulate a plan, which could include continuing as is, modifying the dose of varenicline, or stopping varenicline. If a participant experiences severe side effects, study staff will advise the participant to immediately stop taking varenicline. The study clinician and PI will be notified and will follow-up with the participant within 24 hours to decide with the participant about whether to remain off varenicline or resume the medication at a lower dose. Severe, potentially life-threatening reactions (e.g., cardiac complications) will prompt immediate on-site medical assessment by a health care provider at BHCHP headquarters or at a nearby hospital. The study clinician and PI will be notified and will follow-up with the participant within 24 hours.

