Study staff will also proactively assess suicidality at every on-treatment monitoring visit using a modified version of the C-SSRS (see Appendix 3). Participants at low risk for suicide based on the C-SSRS will be made aware of available behavioral health care resources, including crisis line numbers and on-site mental health services at BHCHP. Participants at moderate risk for suicide based on the C-SSRS will be given 24-hour crisis line numbers and encouraged to schedule a visit with their PCP or an on-site behavioral health provider within 2 business days, with assistance from study staff. The study clinician or PI will call these participants within 24 hours to discuss their suicidality and reinforce the above evaluation plan. Participants at high risk for suicide based on the C-SSRS will be escorted immediately to the on-site BHCHP clinic for an urgent mental health evaluation by BHCHP clinical staff. Study staff will advise these participants to stop varenicline. The study clinician and PI will be notified and will follow-up with

the participant within 24 hours to discuss the plan for moving forward. In instances in which participants show moderate or high risk of suicide based on the C-SSRS, study staff will communicate with participants' PCPs via secure Epic messaging regarding the outcome of this assessment within 2 business days (if moderate risk) or within 24 hours (if high risk). Although suicidality will not be proactively assessed during tobacco coaching sessions, if participants spontaneously bring up suicidal thoughts, the tobacco coach will follow similar procedures to the monitoring visits and assess suicidality risk using the modified C-SSRS and react accordingly based on level of risk.

If a participant misses their monitoring visit, this will trigger an automated text message to their study phone or personal phone advising them to call study staff if they are experiencing any side effects or other concerns related to their participation in the study (see Appendix 1).

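### The monitoring-visit side-effect list in VI.A.3 does not prompt by name for cardiovascular, allergic or serious skin reactions, which VII.B lists as possible varenicline harms

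*Combined protocol and SAP*

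**What the plan says.** Section VI.A sets out the data elements for each visit. Under item 3 (on-treatment monitoring visits) the side-effect entry is "Side effects to varenicline, including abnormal dreams, aggressive/erratic behavior, headaches, nausea, sleep disturbance/insomnia, vomiting, and other", asked at every monitoring visit where applicable. A companion entry covers "Other adverse events not related to varenicline if reported by participant".

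Section VII.B gives the common side effects of varenicline and then adds: "Other possible, but less common, side effects include cardiovascular (chest pain, hypertension, tachycardia), sleep walking, allergic reactions, or serious skin reactions".

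Section IX.C says how reports are graded and handled. "Participants will be asked to rate the severity of their side effects as none, mild, moderate, or severe", and participants are "encouraged to report side effects to varenicline at any time". At the top of the response scale, "Severe, potentially life-threatening reactions (e.g., cardiac complications) will prompt immediate on-site medical assessment". After a missed monitoring visit, "this will trigger an automated text message to their study phone or personal phone advising them to call study staff" if they have side effects or other concerns.

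Section IX.F.1 adds a general assessment for adverse events at every study visit, referring back to VI.A. For participants prescribed varenicline by the study clinician, that assessment includes a standardized checklist. The same section provides for reminders to report problems between visits, related to the study or not. Section V.A.4 has the clinician discuss side effects at weeks 3 and 7, and the coaching record in VI.A.5 takes in "any issues related to safety or potential harms that emerge".

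**The concern.** The list of what staff ask and the list of what the drug may do have not been reconciled. Three groups of harm that the protocol itself considers possible have no named question, and one of them supplies its own example of a life-threatening reaction.

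Attribution is where this matters most. A participant with chest pain or a rash may not think of it as a varenicline side effect and so may not offer it under an open category. If the event is treated as unrelated, the companion entry in VI.A.3 records it only when the participant brings it up. Heart symptoms are the clearest case: section I.A describes heart disease as an important cause of death in this population, so a participant could readily put chest pain down to something else.

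At stake is how promptly such a reaction is mentioned, graded and acted on. That a named question helps with this is a judgement; the document contains no data on it.

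**Working it through.** The plan gives no figure to reproduce on this point, and no incidence or capture rate from which to estimate missed events. The check compares the two lists and then goes through the other routes.

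**Step 1: the lists.** VI.A.3 names abnormal dreams, aggressive or erratic behavior, headaches, nausea, sleep disturbance or insomnia, and vomiting, and ends with an open category. The less common harms in VII.B compare as follows:

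- Sleep walking: can reasonably be recorded as sleep disturbance.
- Cardiovascular (chest pain, hypertension, tachycardia): no named item.
- Allergic reactions: no named item.
- Serious skin reactions: no named item.

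**Step 2: other mentions of the three.**

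- Cardiac complications are named in IX.C, as an example of what triggers immediate medical assessment. That sentence governs the response to a reaction already known; it does not ask about one.
- Allergic reactions to varenicline are named in the exclusion criteria (III.A) and the screening items (VI.A.1), as history before enrollment.
- Serious skin reactions are named only in VII.B.

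**Step 3: the remaining on-treatment routes.**

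- General adverse event assessment at every study visit (IX.F.1): initiated by staff, but it refers back to VI.A and adds no named item.
- Clinician discussion at weeks 3 and 7 (V.A.4): initiated by the clinician, general wording.
- Unrelated events (VI.A.3): recorded if the participant reports them.
- Coach's session record (VI.A.5): open, covering what emerges.
- Reporting at any time, and the text after a missed visit (IX.C): the participant must make contact. IX.C also says the complete checklist is not given by default when a participant phones in.
- Reminders to report problems between visits (IX.F.1): open, with no attribution to the study required.

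None of these routes names any of the three groups in its wording about asking or reporting.

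**Step 4: visits.** Monitoring visits fall at weeks 1 to 8, 10 and 12: 8 + 2 = 10. Clinician follow-up is paired with 2 of them, leaving 10 − 2 = 8 at which the checklist and the general assessment are the staff-initiated side-effect inquiry. With the one-week window, the last clinician visit is at week 7 + 1 = 8 at the latest.

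**Step 5: burden of three added rows.** The document gives no form timings, so 10 to 20 seconds per row is an assumption. Per visit: 3 × 10 = 30 seconds to 3 × 20 = 60 seconds. Over 10 visits: 300 to 600 seconds, or 5 to 10 minutes per participant.

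**The case against.** The strongest reply is that the form itself is not available. The entry in VI.A.3 is worded as open-ended, and the instrument is described elsewhere as a standardized and a complete checklist (IX.F.1 and IX.C). It may already contain these rows, in which case the remedy is editorial. This stands, and it limits the finding to the list as written.

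Staff also already ask. Side effects are solicited proactively at monitoring visits, adverse events are assessed at every study visit, and a clinician reviews tolerance twice. An open question alongside a checklist is a legitimate method. This too stands. A reader might infer that these reactions would go unrecorded, but the document does not support that: the open category can hold them, and several routes do not require the participant to link the event to the drug.

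A reader might also infer that the safety response depends on the participant's rating, so that an unprompted reaction gets no triage. IX.C does not say this. Only its moderate tier is worded in terms of a rating; the severe tier applies to a participant who experiences severe effects, and the life-threatening tier applies to the reaction itself. A rash or chest pain reported under the open category can already be graded and triaged.

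Nor would new rows catch everything. Hypertension may cause no symptom to report, and acute chest pain or a severe allergic reaction between visits would be handled through any-time reporting and urgent assessment, not a question asked a week or two later. Participants are also told the study risks before consent (IX.C), which helps recognition, though it is a single step before treatment.

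What remains is narrower: a symptom the participant does not connect with varenicline and does not think to mention, at a visit where staff are already working through a list.

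**Conclusion.** The point holds as a minor participant-safety improvement. None of the three groups in VII.B is prompted by name in VI.A.3. Across the on-treatment procedures one of the three, cardiac, is named, and only as an escalation example.

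No count of missed events is claimed, and none can be derived from the document. The conclusion assumes that the list in VI.A.3 reflects what staff ask, which cannot be confirmed without the checklist, and that a named question makes a reaction more likely to be mentioned.

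A reader might go on to doubt the efficacy result, but nothing here supports that. Varenicline is offered in both arms, and the 7-day abstinence outcomes rest on self-reported smoking and saliva cotinine, not on side-effect items.

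**What to change.** Add three named rows to the existing checklist and list them in VI.A.3:

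- chest pain or other heart symptoms;
- allergic reaction;
- rash or other skin reaction.

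At each monitoring visit, ask whether each has occurred since the last visit, regardless of whether the participant thinks varenicline was responsible. Use the same four-level severity rating so that the IX.C response applies without change. Keep the open category. If the checklist already has these rows, listing them in VI.A.3 is enough.

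The cost is 0.5 to 1 minute per visit under the timing assumption above, on a form already in use by the same staff. The downside is a few more minor or unrelated reports to log and triage.

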**5) Coaching session data elements: Baseline, 2, 4, 8, and 12 weeks (or within 1 week)**

- Confidence to quit smoking (or to stay quit)
- Importance of quitting smoking (or staying quit)
- Past-month quit attempts
- Summary of coaching session, including experiences delivering the intervention including the ease of delivery (including the length, scheduled time); the apparent acceptability and relevance; comprehension of the material by the participants; and factors that impeded or assisted in the delivery, and any issues related to safety or potential harms that emerge.

## 6) Qualitative interview data elements: 12 and 24 weeks (or within 2 weeks post)

We will create 2 interview guides for incentive arm participants selected for qualitative interviews: one guide to address part A of this aim at 12 weeks, and a second guide to address part B of this aim at 24 weeks. Both will be structured around exploring the cognitive ('why?'), procedural ('how?'), and contextual ('under what circumstances?') dimensions of participants' response (or lack of) to the financial incentives intervention during and after treatment.

• **Cognitive:** Questions in this domain will explore *why* participants abstain (or not) from smoking in response to financial incentives. **A)** At 12 weeks, interviewers will probe: the perceived impact of incentives on smoking cognitions, such as readiness, motivation, and confidence to quit or importance of quitting; the extent to which the extrinsic motivation of incentives was internalized by participants; the importance of incentive dollar amounts, frequency, and format on the perceived potency of incentives; the perceived fairness and understandability of the incentives scheme; and the overall utility of financial incentives in promoting cessation, particularly in relation to other treatments tried by participants. **B)** At 24 weeks, interviewers will probe: how participants coped with transitioning off incentives; how smoking cognitions, such as readiness, motivation, and confidence to quit or importance of quitting, changed following the removal of incentives; and the extent to which participants were successful (or not) in shifting from extrinsic to intrinsic motivational pathways.

• **Procedural:** Questions in this domain will explore *how* participants abstain (or not) from smoking in response to financial incentives. **A)** At 12 weeks, interviewers will probe: participants' use of varenicline and other pharmacotherapies, coaching or other counseling services, or other mainstream or alternative strategies for quitting; how these supplemental strategies facilitated or impeded their response to the incentives intervention; and whether the intervention had spillover effects in promoting related healthy behaviors that reinforced abstinence, such as increasing physical activity or reducing concurrent substance use. **B)** At 24 weeks, the above areas will be explored again, but with a focus on assessing whether these behavioral strategies for sustaining abstinence increased, waned, or remained stable after incentives were removed.

• **Contextual:** Questions in this domain will explore the individual and social *circumstances* under which participants abstain (or not) from smoking in response to financial incentives. At both 12 and 24 weeks, interviewers will probe the ways in which *individual material circumstances*, such as housing status, food security, personal safety, and other basic survival needs; *individual comorbidities*, such as physical ailments, psychiatric symptoms, and concurrent substance use disorders; and *social milieu characteristics*, such as friends who smoke, second-hand smoke exposure, social support for quitting, and access to smoke-free settings, collectively influence **A)** on-treatment abstinence initiation and **B)** post-treatment abstinence maintenance in response to the financial incentives intervention. We will also probe whether and how this relatively 'high-touch' intervention strategy fits within the broader social context of participants' lives in order to optimize the approach for subsequent studies aiming to disseminate and implement this treatment modality.

A third interview guide will be developed for control arm participants that will generically explore their experiences with quitting smoking in the context of homelessness or unstable housing.

